5.1 Screening and Monitoring Evaluations and Measurements

5.1.1 Medical Record Review and demographics questionnaire

- Race
- Ethnicity
- Household income
- Education level
- Blood type
- Calculated panel reactive antibody age
- Time on dialysis
- Diabetes
- Gender
- BMI
- Cause of kidney failure
- Comorbidities (hypertension, cerebrovascular disease, peripheral vascular disease, and malignancy)

5.1.2 Physical Examination

Not applicable

5.1.3 Vital Signs

Not applicable

5.1.4 Laboratory Evaluations

Not applicable

5.1.4.1 Hematology

Not applicable

5.1.5 Other Evaluations, Measures

Not applicable

5.2 Efficacy Evaluations

Baseline and outcome evaluations will be used to test for intervention efficacy. These measures will include: pursuit of transplant, patient knowledge about kidney transplant,

patient decisional conflict, patient hope, social support group knowledge about kidney transplant and social support group intention/motivation to support the patient through the transplant process. A process evaluation will be conducted to ensme the intervention is implemented with fidelity and to assess what worked and did not work dming the implementation process.

5.2.1 Diagnostic Tests, Scales, Measures, etc.

Baseline evaluations will be administered before pruticipation in the intervention. After the intervention is complete, the outcome evaluation smvey will be administered. These smveys will have the same questions and measurements (listed above) in order to test for intervention efficacy/effectiveness.

5.3 Pharmacokinetic Evaluation

Not applicable

5.4 Safety Evaluation

Subject safety will be monitored by the principle investigator.

6 STATISTICAL CONSIDERATIONS

The sample size (n=60) will be sufficient for conducting statistical analysis of the intervention. A Student's T-test will compare means for the primaly outcome of the number of inquiries per candidate. Both a Chi-squared and Student's T-tests will be used to compare secondaly outcomes.

6.1 Primary Endpoint

Prima1y endpoint: pursuit of transplant

6.2 Secondary Endpoints

Secondaty endpoints: patient knowledge about kidney transplant, decisional conflict, and hope. Also, social suppoll group knowledge about kidney transplant and intention/motivation to suppolt the patient through the transplant process

6.3 Statistical Methods

A Student's T-test will compare means for the primaly outcome of the number of inquiries per candidate between and within the intervention and control groups. Both a Chi-squared and Student's T-tests will be used to compare secondruy outcomes between and within the intervention and control groups. This is a feasibility pilot study; therefore, it is not powered to test anything. We will be collecting data that we could adjust for (i.e. demographics), but we will not be adjusting, because the main goal of this particulru study is to gauge if the intervention is feasible.

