3.1.2 Study Intervention

Participants in the intervention group first undergo usual pre-transplant counseling, and will then undergo a group counseling session with members of their suppmt network at the transplant center. The session will include 1) a description of general options for treatment of end stage kidney disease, 2) the likely outcome of each of those options specific to the transplant candidate utilizing the decision aid, 3) a presentation of common reasons to pursue or not pursue each of those options (including common barriers to living donation), and 4) a discussion of how the suppolt network can be involved in the transplant process. Tllis discussion will be infolmed by focus groups conducted in a previous study. The group counseling session will follow a general script and will be facilitated by the principal investigator or a trained transplant educator, with recording and random review of the sessions to ensure quality and consistency of the content. Printed results of the decision aid output will be shared with the clinical transplant team to replicate clinical practice.

The control group will undergo the usual pre-transplant counseling and clinical evaluation conducted by the transplant center team. The control group will be info1med about the availability of the online shared decision aid by a member of the research team.

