3.3.2 Total Number of Study Sites/Total Number of Subjects Projected

The study will be conducted at two investigative sites in the United States.

Recruitment will stop when approximately 60 subjects are consented (7 patients in the control group + 8 patients + 6-7 friends and family each in the intelvention group).

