6.3.2 Efficacy Analysis

The primaly efficacy endpoint will be the change in pursuit of transplant between the baseline and the outcome evaluation. Secondary endpoints will include the change in patient knowledge about kidney transplant, patient decisional conflict, patient hope, social supp01t group knowledge about kidney transplant and social support group intention/motivation to support the patient through the transplant process between the baseline and outcome evaluation. All measurements will be compared with the control/no treatment group measurements.

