6.4 Sample Size and Power

The sample size will be n=60, with 30 patients consented from each site. This is a feasibility pilot study; therefore, it is not powered to test anything.

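### Within-arm significance tests are planned beside the between-arm test, and nothing says that only the between-arm comparison can show an intervention effect

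*Protocol*

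**What the plan says.** Section 6.3 (Statistical Methods) applies Student's t-test to "the number of inquiries per candidate between and within the intervention and control groups". The next sentence says that chi-squared and t-tests "will be used to compare secondruy outcomes between and within the intervention and control groups". The two kinds of comparison share a sentence, and neither is ranked above the other.

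Section 6.3.2 (Efficacy Analysis) defines the primary efficacy endpoint as "the change in pursuit of transplant between the baseline and the outcome evaluation", treats the secondary endpoints as changes too, and adds: "All measurements will be compared with the control/no treatment group measurements". A between-arm comparison is therefore planned. The section does not say that it is the only basis for a statement about efficacy.

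The primary objective in section 2.1 is comparative: whether the counseling increases pursuit of transplant. Sections 6.3 and 6.4 also carry the caveat "This is a feasibility pilot study; therefore, it is not powered to test anything".

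**The concern.** A test of change within one arm asks whether that arm moved from baseline. It does not ask whether the intervention moved it. Three features of the design make movement in both arms plausible without any intervention effect:

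- Usual counseling is common to both arms. Section 3.1.2 says that intervention patients have it first, and for the other arm: "The control group will undergo the usual pre-transplant counseling and clinical evaluation conducted by the transplant center team". Controls are also told about the online decision aid.
- Section 3.3.1 allots the rest of each patient's time on study to standard care and counseling, so some of it can fall after the screening visit where Table 1 places the baseline survey.
- Section 5.2.1 repeats the same questions before and after.

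If both arms improve by a similar amount, chance can make one arm significant and leave the other short of significance. A reader can easily take that pattern as evidence of benefit although the arms do not differ. In a small pilot the between-arm test will seldom be significant, so a within-arm p-value may be the most eye-catching result in the report.

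**Working it through.** **No figure to reproduce.** The protocol states no alpha, sidedness, effect size, SD or power. The calculation therefore rests on assumptions: two-sided alpha 0.05, normally distributed changes, independent arms, and the same true mean change d, in SDs of change, in both arms (no intervention effect).

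**Patients per arm.** The protocol supports two readings.

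- Reading A, section 3.3.2: "7 patients in the control group + 8 patients + 6-7 friends and family each", that is 7 control and 8 intervention patients.
- Reading B, section 6.4: "The sample size will be n=60, with 30 patients consented from each site", that is 60 patients. No allocation ratio is given, so 30 per arm is an assumption.

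**Formula.** For an arm of n patients, the chance p(n, d) of a significant improvement is the probability that a noncentral t variable with n−1 degrees of freedom and noncentrality d√n exceeds the 97.5% point of the central t. The chance of the misleading pattern is

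P(intervention significant, control not) = p_int × (1 − p_ctrl).

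**Reading A (8 v 7)**

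| d | p_int | p_ctrl | p_int × (1 − p_ctrl) |
|---|---|---|---|
| 0 | 0.025 | 0.025 | 2.4% |
| 0.2 | 0.071 | 0.066 | 6.7% |
| 0.4 | 0.164 | 0.144 | 14.0% |
| 0.5 | 0.231 | 0.200 | 18.5% |
| 0.8 | 0.496 | 0.428 | 28.4% |
| 0.87 (peak) | 0.563 | 0.489 | 28.8% |
| 1.0 | 0.681 | 0.601 | 27.2% |
| 1.2 | 0.828 | 0.754 | 20.4% |
| 1.5 | 0.951 | 0.908 | 8.8% |

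**Reading B (30 v 30, assumed)**

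| d | p per arm | p × (1 − p) |
|---|---|---|
| 0 | 0.025 | 2.4% |
| 0.2 | 0.184 | 15.0% |
| 0.37 (peak) | 0.500 | 25.0% |
| 0.5 | 0.754 | 18.6% |
| 0.8 | 0.989 | 1.1% |

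**Between-arm test.** Simulation with 200,000 trials per setting (d from 0 to 1.0, both readings) gave a pooled two-sample t-test that was significant in 4.9% to 5.1% of trials, whatever the common change. Under reading A with d from 0.5 to 1.0, that test was non-significant in 89% to 93% of the trials that showed the misleading pattern. The usual outcome would thus be a null randomised comparison beside an apparently positive within-arm contrast.

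**Baseline for the primary outcome.** Table 1 assesses the primary outcome from medical records at follow-up only. Section 5.2 lists pursuit of transplant among the baseline and outcome measures, but the patient survey in the appendix has no item on it. A within-arm test of inquiries therefore has no scheduled baseline.

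**Supporter outcomes.** Section 3.3.2 counts friends and family only in the intervention group. If that is how they are enrolled, their knowledge and intention to support can only be compared with their own baseline, with no control.

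**The case against.** The best defence is that the randomised comparison is already in the plan. Section 6.3.2 compares all measurements with control, section 1.1 describes the trial as group counseling against usual care, and no section says that efficacy will be concluded from a within-arm p-value. Ranking of tests may also be left to an SAP that is not shown. This stands as far as it goes. A reader might infer that the protocol gives both kinds of test equal standing or means to claim benefit from within-arm results, and the text supports neither. But section 6.3 itself prescribes the within-arm tests, so the wording can be corrected there.

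The second objection is that the size depends on unknowns. That also stands. The common change is not given in the document, the pattern is rare (2.4%) when neither arm changes, and under the 60-patient reading it nearly disappears once d reaches 0.8.

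Three further inferences are tempting and should not be drawn:

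- That inquiries must start at zero, so that the within-arm test is bound to show a rise. The protocol neither defines inquiries nor says when they can begin, so no count model is used here.
- That the 8 v 7 imbalance drives the result. At d=0.8 the pattern occurs in 28.4% with 8 v 7 and 25.0% with 8 v 8, so one patient adds little.
- That the chance of exactly one significant arm (up to about 50% under reading A) measures false claims of benefit. At d=0.8 about 22 of those 50 points are trials in which only the control arm is significant.

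Finally, the feasibility label lowers the stakes. It does not make the within-arm p-values interpretable, and section 2.1 still sets an efficacy objective.

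**Conclusion.** The point holds in a limited form. Section 6.3 calls for within-arm tests that cannot answer the comparative objective, and no section restricts them to description. If the two arms share a moderate change, the pattern of improvement in the intervention arm only can appear in up to about 29% of trials with 8 v 7 patients, or 25% with an assumed 30 per arm, against 5% for the between-arm test. These figures rest on the assumed alpha, normality and common change. They are maxima within a range that starts at 2.4% and falls again when the common change is large. For inquiries, the within-arm test also lacks a scheduled baseline.

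Severity is minor to moderate: a between-arm comparison is already planned and the study is labelled a feasibility pilot.

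**What to change.** 1. In section 6.3, delete *and within* from both sentences.
2. State that intervention effects are judged only from the between-arm difference, in outcome or in change, reported with a 95% CI.
3. Report within-arm change descriptively: mean change with a CI and no p-value. For inquiries, do so only if a baseline count is added to Table 1; otherwise compare follow-up counts between arms.
4. If friends and family are enrolled only in the intervention group, as section 3.3.2 reads, report their outcomes as uncontrolled descriptive change and make no efficacy claim from them.

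The cost is wording only. No visits, patients or data need to be added, and there are fewer tests to run.

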3.2 Allocation to Groups and Blinding

The enrolled study participants will be randomized via computer into either the intervention or control group. Palticipant and researcher blinding is not feasible for the intervention, but asceltainment and statistical analysis of outcomes will be performed by an analyst blinded to group assignment.

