21. I have a deep inner strength.

- D Strongly agree
- D Agree
- D Disagree
- D Strongly disagree

22. I an1able to give and receive caring/love.

- D Strongly agree
- D Agree
- D Disagree
- D Strongly disagree
- 23. I have a sense of direction.
 - D Strongly agree
 - D Agree
 - D Disagree
 - D Strongly disagree
- 24. I believe that each day has potential.
 - D Strongly agree

D Agree

D Disagree

D Strongly disagree

25. I feel my life has value and wo1ih.

- D Strongly agree
- D Agree
- D Disagree
- D Strongly disagree

26. How confident are you filling out medical f01ms by yourself?

- D Extremely
- D Quite a bit
- D Somewhat
- 0 A little bit
- D Not at all

Family Survey

- **1.** A patient on dialysis has the same level of kidney functioning as a patient with a transplanted kidney.
 - D Trne
 - D False
 - D Don't know
- 2. In general, patients can live at least 5 years longer with a kidney transplant than if they stayed on dialysis.
 - D Trne
 - D False
 - D Don't know
- 3. In general, most people on dialysis are happier with the quality of their lives than people with transplants.
 - D Trne
 - D False
 - D Don't know
- 4. Patient have better health outcomes if they receive a transplant before staling dialysis.
 - D True
 - D False
 - D Don't know
- 5. If a patient waits long enough on the waitlist, a matching kidney from someone who has died will definitely become available.
 - D Trne
 - D False
 - D Don't know

- 6. About what percentage of all transplanted kidneys function for at least one year?
 - 0 50%
 - 0 75%
 - 0 90%
 - D Don't know
- 7. Nationally, how long do patients generally wait on the wait list for a kidney from someone who has died?
 - D < 1 year
 - D 1-2 years
 - D 3-5 years
 - D > 5 years
 - D Don't know
- 8. Compared to transplants from donors who have died, how long do transplants from living donors last?
 - D Sh01ter
 - D Longer
 - D Same
 - D Don't know
- 9. What is the chance that a living donor or recipient would dies undergoing surgery?
 - □<1%
 - 3%
 - □ 10%
 - 0 25%
 - D Don't know

- 10. I am confident that I could deal efficiently with unexpected events.
 - D Never
 - D Ahnost never
 - D Sometimes
 - D Fairly often
 - D Ve1yoften
- 11. I intend to help my friend or family member get through the transplant process.
 - D Strongly agree
 - D Agree
 - D Neither agree nor disagree
 - D Disagree
 - D Strongly disagree
- 12. A.re you seriously thinking about helping my friend or family member get through the transplant process?

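### The two supporter endpoints are assigned ordinary t and chi-squared tests, with no provision for 6-7 friends and family sharing one candidate and one session

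*Protocol*

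**What the plan says.** Section 6.2 lists five secondary endpoints. Three are patient endpoints and two are supporter endpoints: "social suppoll group knowledge about kidney transplant and intention/motivation to suppolt the patient through the transplant process". Section 6.3.2 defines the supporter endpoints as changes, for example in "social support group intention/motivation to support the patient through the transplant process between the baseline and outcome evaluation".

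Section 6.3 gives one method for all secondary outcomes: "Both a Chi-squared and Student's T-tests will be used to compare secondruy outcomes between and within the intervention and control groups". It does not say whether the within-group tests are paired, or whether the supporter or the candidate is the unit of analysis.

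Three other places fix the structure of the supporter data:

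- **Group size (Section 3.3.2).** Recruitment is described as "7 patients in the control group + 8 patients + 6-7 friends and family each in the intelvention group". No supporters are listed for control patients.
- **Shared exposure (Section 3.1.2).** After usual counselling, intervention participants "will then undergo a group counseling session with members of their suppmt network at the transplant center". The session presents outcomes specific to that candidate.
- **Measurement (Section 11, Family Survey).** Items are answered person by person, for example "I intend to help my friend or family member get through the transplant process".

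On allocation, Section 3.2 says: "The enrolled study participants will be randomized via computer into either the intervention or control group". Supporters are listed by candidate, so they follow their candidate's assignment.

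**The concern.** Student's t and the chi-squared test both assume independent observations. A candidate's supporters come from one family or circle of friends, sit in the same discussion and hear the same facilitator, so their changes may plausibly be correlated. With any positive correlation, a paired t-test on individual changes uses a standard error that is too small.

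A few cohesive groups could then be reported as a significant gain in supporter knowledge or motivation. A follow-on trial that took its variability from this pilot would also start from too small a standard error.

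**Working it through.** **Inputs from the protocol.** 8 intervention candidates with 6-7 supporters each (Section 3.3.2), which gives 48 to 56 supporters, midpoint 8 × 6.5 = 52. The test type is from Section 6.3 and the change-score endpoint from Section 6.3.2.

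**Assumptions not in the protocol.** Two-sided 5% level; ICC of change scores from 0.01 to 0.30. The ICC of change is the relevant one, because stable differences between families cancel when each person's baseline is subtracted.

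**The plan's own total.** Section 3.3.2 gives approximately 60. Its components give 7 + 8 + 8 × 6 = 63, 7 + 8 + 52 = 67, or 7 + 8 + 8 × 7 = 71. Reaching 60 would need 45/8 = 5.6 supporters per candidate. This mismatch, and the 60 patients in Section 6.4, are separate matters. The design effect below depends on group size, not on the number of groups, so settling the total would not remove the problem.

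**Formulas**, with m = 6.5:

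- Design effect: DE = 1 + (m − 1) × ICC
- Factor by which the ordinary standard error is too small: √DE
- Effective number of supporters: 52/DE
- Approximate actual error: 2 × [1 − Φ(1.96/√DE)]

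At ICC 0.10, for example, DE = 1 + 5.5 × 0.10 = 1.55, √DE = 1.24, effective n = 52/1.55 = 34, and the actual error is 11.5%.

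The last two columns are from a simulation with no true effect: 20,000 runs of 8 groups alternating 6 and 7 members. They compare a t-test on 52 individual changes with a t-test on the 8 candidate means.

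| ICC of change | DE | SE factor | Effective n | Error, formula | Error, individual t | Error, candidate means |
|---|---|---|---|---|---|---|
| 0.01 | 1.06 | 1.03 | 49 | 5.6% | 5.5% | 5.0% |
| 0.05 | 1.28 | 1.13 | 41 | 8.3% | 8.2% | 5.1% |
| 0.10 | 1.55 | 1.24 | 34 | 11.5% | 11.3% | 5.0% |
| 0.20 | 2.10 | 1.45 | 25 | 17.6% | 17.6% | 5.0% |
| 0.30 | 2.65 | 1.63 | 20 | 22.9% | 23.4% | 5.1% |

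**Chi-squared.** For an item answered yes by about half of supporters, compared with 7 hypothetical control groups of 6-7, the simulated error is 7.1%, 8.8%, 13.8% and 17.6% at ICC 0.05, 0.10, 0.20 and 0.30. The ICC here is that of the underlying continuous score before it is cut into yes and no. The inflation is smaller than for the t-test, but in the same direction.

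**If the pre/post t-test were unpaired.** At ICC 0.10 the simulated error is 6.1%, 2.7% and 0.5% for pre-post correlations of 0.3, 0.5 and 0.7. Ignoring the pairing pushes the error the other way.

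**The case against.** **The unit of analysis is not stated.** A t-test on candidate means is also a Student's t-test, and calling the endpoints those of the social support group does not exclude one value per group. Such detail is often left to an SAP, and none is at hand. This stands in part: the person-level reading is an inference. It is the natural one, because the survey is individual, Section 3.3.2 reaches its total by counting supporters one by one, and the opening of Section 6 calls that total sufficient for statistical analysis. The protocol also names the tests, so the method has been fixed without a condition these data need. An SAP that specified candidate-level analysis would settle the point.

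**The size is uncertain.** The general script and the review of recorded sessions work against differences between sessions, and the knowledge items are general facts. A low ICC is possible, and at 0.01 nothing of consequence follows. This stands.

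**It is a pilot.** Sections 6.3 and 6.4 disclaim power, Section 6.3 gives feasibility as the main goal, and no significance level or success rule is set. That limits the harm. It does not make the standard error right, and low power is a different matter from an invalid test.

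A reader might infer three stronger things that the protocol does not support:

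- **That clustering adjustment is ruled out.** Section 6.3 says "we will not be adjusting, because the main goal of this particulru study is to gauge if the intervention is feasible", but the sentence concerns covariates such as demographics, not correlation among supporters.
- **That a planned between-arm supporter comparison is inflated.** Section 6.3.2 says all measurements are compared with control, but Section 3.3.2 lists no control supporters. Clustering would affect that comparison only if control supporters were surveyed.
- **That the error must be anti-conservative whatever test is run.** Section 6.3 does not say the within-group test is paired, and an unpaired test can be conservative. The change-score definition in Section 6.3.2 favours pairing, and the inflation figures are conditional on it.

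**Conclusion.** The point holds in a limited form. As written, the plan assigns tests that assume independence to supporter outcomes nested in 8 candidates, with no provision for the nesting. For a paired t-test on individual supporter changes, the nominal 5% error becomes about 8% to 23% if the ICC of change is 0.05 to 0.30, and stays at about 5.5% if it is 0.01. The ICC range, the 5% level and the person-level unit are assumptions; the group structure and the named tests come from the protocol.

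The effect is confined to two of the five secondary endpoints and, as recruitment is described, to the within-intervention comparison. The primary outcome and the patient endpoints have one record per candidate and are unaffected. It should be corrected because the remedy is cheap, but it does not undermine the pilot's feasibility aim.

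**What to change.** In Sections 6.3 and 6.3.2, state that supporter outcomes are analysed with the candidate as the unit: average the supporters' changes (or take the proportion answering yes) within each candidate, then analyse one value per candidate. With 8 intervention candidates that is a t-test on 8 − 1 = 7 degrees of freedom. A mixed model with a candidate random intercept and small-sample degrees of freedom is an acceptable alternative. If control supporters are to be surveyed, say so, and apply the same rule to the between-arm comparison. Report the ICC of change, which a follow-on trial would need.

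The cost is one or two sentences and no new data. The price is a wider confidence interval for the two supporter endpoints.

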9.2 Data Collection and Management

We will keep a master list containing all PHI and subject ID numbers separate from data fo1ms that have only a study ID number. The master list will be in a locked file cabinet. We will keep a copy of all data on REDCap, a password protected electronic database which meets Health fusurance Po1tability and Accountability Act (HIPAA) and University security requirements, with the original paper copy locked in a cabinet.

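### Section 6.3 gives within-arm before/after comparisons the same chi-squared and Student's t-tests as between-arm ones: ordinary chi-squared is wrong for paired yes/no answers, and the t-test is never said to be paired

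*Protocol*

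**What the plan says.** Section 6.3 of the Protocol fixes the tests. For the primary outcome: "A Student's T-test will compare means for the primaly outcome of the number of inquiries per candidate between and within the intervention and control groups". For the secondary outcomes, chi-squared and Student's "T-tests will be used to compare secondruy outcomes between and within the intervention and control groups". The synopsis and the opening of section 6 name the same tests. None of these places mentions a paired t-test, McNemar's test or any other method for dependent data.

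Section 5.2.1 describes how the survey data arise. "Baseline evaluations will be administered before pruticipation in the intervention", an outcome survey follows the intervention, and "These smveys will have the same questions and measurements (listed above) in order to test for intervention efficacy/effectiveness". Section 6.3.2 defines the secondary endpoints as changes from baseline to the outcome evaluation, and does the same for the primary one: "The primaly efficacy endpoint will be the change in pursuit of transplant between the baseline and the outcome evaluation".

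The appendix surveys contain yes/no items (patient items 10 to 13, family item 12) as well as items that would be summed to scores.

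**The concern.** A within-arm comparison here sets each person's second answer against that person's first. The two are normally correlated, and a valid standard error for the change has to use that correlation.

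The ordinary chi-squared test cannot use it. It would treat 8 people answering twice as 16 independent respondents. A two-sample t-test makes the same mistake with scores. Section 6.3 assigns one list of tests to both kinds of comparison, so an analyst who follows it literally could apply the between-arm form within arms.

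What is at stake is the stated precision of within-arm change. This matters most for friends and family: section 3.3.2 places them only in the intervention group, so before/after change is the only comparison available for them.

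**Working it through.** **No figure to reproduce.** The protocol gives no alpha, SD, effect size, within-person correlation or power. The following are therefore assumptions: two-sided 5%, equal SDs before and after, bivariate normal scores, correlation rho of 0.3 to 0.7, and a true change of 0.5 SD.

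**Sample size.** The protocol describes it in two ways. Section 3.3.2 has 7 control patients, 8 intervention patients, and 6-7 friends and family for each intervention patient. Section 6.4 has 60, with 30 patients from each site. Both n = 8 and n = 30 per arm are shown; the latter assumes equal allocation of 60 patients.

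**Standard error of mean change.**
- Paired: SD x sqrt(2(1 - rho)/n)
- Unpaired: SD x sqrt(2/n)
- Ratio, unpaired to paired: 1/sqrt(1 - rho)
  - rho 0.3: 1/sqrt(0.7) = 1.20
  - rho 0.5: 1/sqrt(0.5) = 1.41
  - rho 0.7: 1/sqrt(0.3) = 1.83
- At rho = 0 the ratio is 1 and nothing is lost.

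**t-tests for scores.** Simulated with at least 40,000 replicates; the paired powers agree with the exact noncentral t.

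| n | rho | Type I error, unpaired | Type I error, paired | Power, unpaired | Power, paired |
|---|---|---|---|---|---|
| 8 | 0.5 | 1% | 5% | 9% | 23% |
| 8 | 0.7 | 0.3% | 5% | 6-7% | 35% |
| 30 | 0.5 | 0.7% | 5% | 47% | 75% |
| 30 | 0.7 | 0.1% | 5% | 47% | 93% |

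**Chi-squared for yes/no items.** Type I error was computed with 50% answering yes both times, and power with a rise from 50% to 70%. The correlation is that of an underlying normal variable. Here McNemar is the uncorrected chi-squared version.

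| n | Latent rho | Type I error, chi-squared | Type I error, McNemar | Power, chi-squared | Power, McNemar |
|---|---|---|---|---|---|
| 8 | 0.5 | 2.9% | 2.6% | 12% | 11% |
| 8 | 0.8 | 0.7% | 0.7% | 7% | 7% |
| 30 | 0.5 | 1.7% | 4.1% | 32% | 44% |
| 30 | 0.8 | 0.2% | 4.7% | 28% | 62% |

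With 8 pairs McNemar gains no power. The exact test needs at least 6 discordant pairs, all in one direction: 2 x 0.5^6 = 0.031, whereas five give 2 x 0.5^5 = 0.063.

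**Friends and family.** Take 6.5 relatives per patient and an assumed intraclass correlation (ICC) of change of 0.1 to 0.3. The design effect is 1 + 5.5 x ICC, that is 1.55 to 2.65. A paired interval that ignores clustering then understates the SE by a factor of sqrt(1.55) = 1.24 to sqrt(2.65) = 1.63.

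An analysis that ignores both pairing and clustering states an SE that is 1/sqrt((1 - rho) x design effect) times the true one. At rho 0.5 this is 1/sqrt(0.775) = 1.14 for ICC 0.1 and 1/sqrt(1.325) = 0.87 for ICC 0.3. The direction of the error is therefore not fixed for these outcomes.

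**The case against.** The best reply concerns the t-test. Student's t-test is a family name that includes the paired form, and nothing in the protocol says two-sample or unpaired. Section 6.3.2 defines the endpoints as change, and a t-test on change uses each person's own difference. This stands. It limits the t-test part to an ambiguity in the wording.

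A reader might go further and infer that the SD of change will never be produced. The documents do not support that: the change endpoints in section 6.3.2 could yield it, and study IDs on the data forms (section 9.2) allow the two surveys to be linked.

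A second reply is that choosing the form of a named test belongs in the statistical analysis plan. That is fair for scoring and for the t-test. It does not rescue the chi-squared test, which the protocol itself names for within-arm use.

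A third reply is that little depends on this. Sections 6.3 and 6.4 say the study is not powered to test anything, and no decision rule uses a within-arm p-value. With 8 patients, McNemar is no more powerful than chi-squared. This keeps the point minor, but does not make a test that assumes independence suitable for paired answers.

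It is also tempting to say that the error is always conservative. That holds for patients under positive correlation. It is not established for relatives, where clustering pushes the other way.

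**Conclusion.** The point holds in limited form. As written, section 6.3 prescribes a wrong test for within-arm yes/no items, provided chi-squared means the ordinary Pearson test. For scores it leaves open an unpaired analysis that the change endpoints argue against.

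If the unpaired t-test were used, real change in patients would be missed rather than falsely found: the SE of change would be 41% too large at correlation 0.5 and 83% too large at 0.7. These sizes rest on the assumed correlations, 0.5 SD change, 5% level and sample sizes, none of which the protocol settles. Between-arm comparisons are untouched. This is a minor, easily corrected fault in an unpowered feasibility pilot.

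**What to change.** In section 6.3, separate the two kinds of comparison:

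- **Between arms:** keep the independent-samples tests here only.
- **Within arm, scores:** use a paired t-test on each person's difference, reporting mean change, SD of change and a 95% CI.
- **Within arm, yes/no items:** report discordant pairs with exact McNemar, called descriptive if there are only 7-8 patients per arm.
- **Friends and family:** compute the interval for change allowing for clustering within the patient, for example from the mean change per patient.

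The cost is wording and slightly more analysis. No new data are needed, because the same surveys are already planned before and after. The interval for the family outcomes will be wider than one that ignores clustering.
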